10.3 Analysis Datasets

Data will be pooled from all study centers for data analysis, unless otherwise specified. Study dataset will be generated (keypunched) from original (white) case report forms that have been reviewed and collected from clinical sites. Dataset will contain rows of individual subject data; each row will be clearly labeled with the study subject ID number and initials. Each column of the dataset will contain a specific parameter for all study subjects.

10.4 Description of Statistical Methods

10.4.1 General Approach

All statistical tests will be two-sided and interpreted at a 5% significance level. Descriptive statistics (i.e., mean, standard deviation, etc.) will be provided for all continuous variables and frequency distributions will be generated for all categorical variables collected in this study.

10.4.2 Analysis of the Primary Endpoint(s)

The primary study variable will be based on the change from baseline in tear lake values. For analyses, using the intent-to-treat (ITT) data set, all data from all subjects with at least one follow-up evaluation of the tear lake will be evaluated. For the per protocol (PP) analyses dataset, data from subjects or visits with significant protocol deviations will be excluded.

10.4.3 Analysis of the Secondary Endpoint(s)

Secondary endpoints will be based on changes from baseline in the severity of epiphora. For the investigator's evaluation of the subject's acceptance of the punctal plug, data from all subjects will be evaluated. Investigator evaluation of insertion and removal characteristics will be tabulated by study subject and overall evaluation. For analyses using the intent-to-treat (ITT) data set, all data from all subjects with at least one assessment of epiphora, subject acceptability and punctal plug characteristics evaluations will be included. For the per protocol (PP) analyses dataset, data from subjects or visits with significant protocol deviations will be excluded.

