- e. Slit-Lamp examination of the planned study eye, prior to the sizing and dilation of the lower punctum
- f. Tear lake evaluation of the planned study eye, prior to the sizing and dilation of the lower punctum
- g. Size evaluation of the lower puncta of the planned study eye, prior to dilation of the lower punctum
- h. After dilation of the punctum to at least 1.0 mm, insert the study punctal plug
- i. Inspection of the punctal plug after insertion via slit-lamp
- j. Record any Adverse Device Events
- k. After a study subject has been inserted with the NDE L68 StableFit® punctal plug, the Investigator will evaluate the insertion characteristics of the punctal plug

NOTE: After the last study subject has been inserted with a study punctal plug, based on all subjects enrolled in the study, the investigator will give an overall assessment on the insertion characteristics of the study punctal plug.

Visit 2: Follow-up (Day 7 + 1 post plug insertion)

- a. Verify a subject has not used any ocular drops, in their study eye, within the last hour prior to their scheduled visit
- b. Slit Lamp examination
- c. Inspection of the plug via slit-lamp
- d. Tear lake evaluation
- e. Record any Adverse Device Events

Visit 3: Follow-up (Day 28 + 4 post plug insertion)

- a. Verify a subject has not used any ocular drops, in their study eye, within the last hour prior to their scheduled visit
- b. Investigator evaluation of the subject's acceptability of the punctal plug, prior to removal of the study plug
- c. Slit Lamp examination, prior to removal of the study plug
- d. Inspection of plug via slit-lamp, prior to removal of the study plug

- e. Tear lake evaluation, prior to removal of the study plug
- f. Remove study punctal plug
- g. After the plug has been removed, the Investigator will evaluate the removal characteristics of the inserted punctal plug
- h. Record any Adverse Device Events

NOTE: After the last study subject has had their punctal plug removed, based on all subjects that completed the study, the investigator will give an overall assessment on the removal characteristics of the punctal plug.

Study Outcome Variables:

Primary Study Endpoint: Investigators' evaluation of the tear lake

Secondary Study Endpoint: Investigator's evaluation of epiphora, insertion/ removal characteristics and Investigators' evaluation of the subject's acceptance of the NDE L68 StableFit® punctal plug.

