Study Safety Variables: Safety assessments will include any clinically significant slit-lamp biomicroscopy findings, any extrusions of a punctal plug and incidence and severity of any reported ADEs after punctal plug insertion.

Sample Size Determination: Since this is a pilot study, no formal sample size estimation was performed.

Schedule of Assessments, Events

EXAM PARAMETERS	v1	v2	v3
Inform Consent/HIPAA	①		
Demographic Data/Medical Hx	① A		
Subject Reports of any Ocular Signs or Symptoms	① B		
Verify No Ocular Drop use One Hour Prior to Visit	①	②	③
Inv. Evaluation of Subject's Acceptance of Study Plug			③ C
Slit Lamp Examination	① B	②	③ C
Tear Lake Evaluation	① B	②	③ C
Size Evaluation of Lower Puncta, Prior to Dilation	① B		
Dilation of Lower Puncta	①		
Insertion of a Punctal Plug	①		
Inspection of the Placement of the Punctal Plug	① D	②	③ C
Investigator Device Assessment of Insertion	① E		
Removal of Punctal Plug			③
Investigator Device Assessment of Removal			③ F
Adverse Device Event Recording	①	②	③

Keys to Abbreviations:

A = Record medical history for the past 7 days

B = PRIOR to **INSERTION** of punctal plug

C = PRIOR to **REMOVAL** of punctal plug

D = Slit-Lamp Evaluation of Punctal Plug **AFTER INSERTION**

E = After EACH Study Subject and after **ALL** Study Subjects have had their Punctal Plug Inserted

F = After EACH Study Subject and after **ALL** Study Subjects have had their Punctal Plug Removed

Visit Schedule:

v1 = Screening/Baseline

v2 = 7 ± 1 days post plug insertion

v3 = 28 ± 4 days post plug insertion

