4.2.2 Secondary Study Endpoints

Secondary study endpoints will evaluate the investigator's evaluation of epiphora, insertion/removal characteristics of the NDE L68 StableFit® punctal plug, and Investigators' evaluation of the study subjects' acceptance of the NDE L68 StableFit® punctal plug.

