7.3 Study Visit Schedule

7.3.1 Visit 1: Day 0 - Screening (Prior to punctal plug insertion)

A potential study subject qualifications will be assessed according to the inclusion/exclusion criteria listed in the protocol (see Sections 5.2 and 5.3). Prior to undergoing any study-specific procedures, both the study Informed Consent and Authorization for Use/Disclosure of Health Information forms (HIPAA authorization) must be signed by a potential subject who has agreed to participate in the study. During this visit, the following information will be collected/evaluated and recorded in the appropriate sections of the study case report forms of a subject, prior to the sizing and dilation of the lower punctum for the planned study eye.

- a. Obtain informed consent and HIPAA authorization release
- b. Record the subject's demographic data and prior 7 days medical history
- c. Verify a subject has not used any ocular drops within the last hour prior to their baseline visit
- d. Record any subject reports of ocular signs or symptoms they are currently experiencing
- e. Slit-lamp examination of the planned study eye

7.3.2 Visit 1:Baseline - Day 0 (Insertion of a punctal plug - refer to Section 6.2 for details regarding the insertion of the NDE punctal plug)

After the screening examination, a qualified study subject will be sequentially assigned an ID number. In addition, the ID number and the study subject initials will be recorded on study case report forms, in lieu of recording his/her name, in order to maintain subject confidentiality.

Note: The investigator has the option of inserting the plug in either the left or right eye of the subject. However, if the investigator is unable to insert the plug in the first eye chosen, the investigator can insert the plug in the fellow eye as long as the fellow eye meets all study inclusion/exclusion criteria.

- f. Tear lake evaluation of the planned study eye prior to the sizing and dilation of the lower punctum
- g. Size evaluation of the punctum of the planned study eye prior to the dilation of the lower punctum
- h. After dilation, the study punctal plug is inserted in to the lower punctum of study eye, inspect the punctal plug using the slit-lamp, the position of a study punctal plug may be adjusted with forceps.
- i. Record any reported adverse device event(s)

j. After the study plug has been inserted in the lower puncta, the investigator will assess the insertion characteristics of the plug.

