7.3.4 Visit 3: Follow-Up (Day 28 + 4 post plug insertion)

At this visit the following will be performed and recorded:

- a. Verify a subject has not used any ocular drops, in their study eye, within the last hour prior to their scheduled visit
- b. Investigator evaluation of subject's acceptability of the punctal plug, prior to the removal of the punctal plug
- c. Slit-lamp examination, prior to the removal of the punctal plug
- d. Inspection of the punctal plug via the slit lamp, prior to removal of the plug
- e. Tear lake evaluation of the eye prior the removal of the punctal plug
- f. Removal of the punctal plug (refer to [Section 6.6](#) for details regarding the removal of a punctal plug)
- g. Recording of any reported adverse device event
- h. After removal of the study subject punctal plug, the investigator will assess the removal characteristics of the plug.

NOTE: After the last study subject has had their punctal plug removed, the investigator will give an overall assessment on the removal characteristics of all punctal plugs that were inserted during the study.

An exit form will be completed at the final study examination (Visit 3), or whenever the study subject completes or leaves the study for any reason.

Schedule of Assessments, Events

EXAM PARAMETERS	v1	v2	v3
Inform Consent/HIPAA	①		
Demographic Data/Medical Hx	① A		
Subject Reports of any Ocular Signs or Symptoms	① B		
Verify No Ocular Drop use One Hour Prior to Visit	①	②	③
Inv. Evaluation of Subject's Acceptance of Study Plug			③ C
Slit Lamp Examination	① B	②	③ C
Tear Lake Evaluation	① B	②	③ C
Size Evaluation of Lower Puncta, Prior to Dilation	① B		
Dilation of Lower Puncta	①		
Insertion of a Punctal Plug	①		
Inspection of the Placement of the Punctal Plug	① D	②	③ C
Investigator Device Assessment of Insertion	① E		
Removal of Punctal Plug			③
Investigator Device Assessment of Removal			③ F
Adverse Device Event Recording	①	②	③

Keys to Abbreviations:

- A = Record medical history for the past 7 days
- B = PRIOR to **INSERTION** of punctal plug
- C = PRIOR to **REMOVAL** of punctal plug
- D = Slit-Lamp Evaluation of Punctal Plug **AFTER INSERTION**
- E = After EACH Study Subject and after **ALL** Study Subjects have had their Punctal Plug Inserted
- F = After EACH Study Subject and after **ALL** Study Subjects have had their Punctal Plug Removed

Visit Schedule:

- v1 = Screening/Baseline
- v2 = 7 ± 1 days post plug insertion
- v3 = 28 ± 4 days post plug insertion

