10.2.2 Secondary Hypotheses

The Null Hypothesis: There are no differences in the frequency or severity of study subjects exhibiting of epiphora

Alternative Hypothesis: There are differences in the frequency or severity of study subjects exhibiting of epiphora

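### Investigator-evaluated epiphora is a secondary endpoint and the only secondary hypothesis, but the protocol schedules no evaluation of it after insertion and names no scale or data source

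*Combined protocol and SAP*

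**What the plan says.** The synopsis lists the investigator's "evaluation of epiphora, insertion/ removal characteristics" among the secondary endpoints. Section 4.2.2 agrees: "Secondary study endpoints will evaluate the investigator's evaluation of epiphora". Section 10.2.2 gives one secondary null hypothesis: "There are no differences in the frequency or severity of study subjects exhibiting of epiphora".

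Section 10.4.3 sets the analysis variable: "Secondary endpoints will be based on changes from baseline in the severity of epiphora". For the ITT set it adds that "all data from all subjects with at least one assessment of epiphora, subject acceptability and punctal plug characteristics evaluations will be included". The analysis plan therefore takes for granted that an epiphora assessment exists.

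The other secondary measures have places in the visit lists and in both copies of the Schedule of Assessments. An example is the row "Inv. Evaluation of Subject's Acceptance of Study Plug", marked at Visit 3. The nearest row to epiphora is "Subject Reports of any Ocular Signs or Symptoms", marked at Visit 1 only. It matches item (d) of section 7.3.1: "Record any subject reports of ocular signs or symptoms they are currently experiencing".

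Apart from its role as endpoint and hypothesis, epiphora appears only as exclusion criterion (g), in the synopsis and section 5.3, and as a listed risk of punctal plugs in section 2.3.

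**The concern.** A change from baseline in severity needs a graded value at baseline and at follow-up, on one scale. A comparison of frequency needs to know, for each subject at each visit, whether epiphora was looked for. A site that follows the visit lists exactly would make no solicited investigator evaluation of epiphora at Day 7 or Day 28.

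Where nothing is recorded, the analyst cannot tell a subject without epiphora from one who was not assessed. The answer to the only secondary hypothesis would then turn on a convention for reading blanks that the plan does not state. Section 2.3 names epiphora as a known risk of plug use, so under-recording would understate a relevant device effect. A missed visit assessment cannot be recovered once the visit has passed.

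**Working it through.** The plan gives no figure to reproduce here, so the check is a comparison of text.

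**Step 1: what is scheduled.** Sources are the synopsis visit lists, sections 7.2.1 and 7.3.1 to 7.3.5, and both Schedules. Early exit is covered only in 7.3.5.

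| Measure | Visit 1 | Visit 2 | Visit 3 | Early exit |
|---|---|---|---|---|
| Tear lake (primary) | yes | yes | yes | yes, if plug not extruded |
| Insertion characteristics | yes | – | – | – |
| Acceptance | – | – | yes | yes, if plug not extruded |
| Removal characteristics | – | – | yes | yes |
| Epiphora | eligibility only, no grade | no | no | no |

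Epiphora evaluations scheduled after insertion: 0 of 3 (Visit 2, Visit 3, early exit). The minimum list for unscheduled visits (7.3.6) has none either.

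**Step 2: baseline.** Section 7.3.1 has eligibility assessed at Visit 1, and exclusion (g) rules out epiphora. The synopsis applies (g) to the planned study eye and section 5.3 to either eye. Under both, the study eye starts without epiphora. A fellow eye used after a failed insertion must also meet the criteria. Baseline is thus an implied, ungraded *none*, and the gap lies at follow-up. Change from baseline can then go in one direction only, so it reduces to post-insertion incidence and severity.

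**Step 3: could another scheduled procedure supply the value?**
- *Slit lamp* (7.2.1 d): lid, conjunctiva and cornea, each normal or abnormal. Epiphora is not among them.
- *Tear lake* (7.2.1 e): a height in millimetres, not a rating of epiphora.
- *Symptom reports*: from the subject, at Visit 1 only in the lists and Schedules.
- *Source notes* (11.1 h): subject-reported signs and symptoms at every visit. Section 10.3 has the dataset keypunched from CRFs, so the notes reach the analysis only through a CRF item.
- *Adverse device events* (7.2.1 i, 8.1, 8.3.1, 8.5, 10.4.4): epiphora reported or observed after insertion could be recorded, graded and tabulated by visit. But the prompt is a general question about problems since the last visit, and the intensity scale starts at mild. Section 10.4.3 does not name these records as the endpoint source. Section 8.6.4 calls plug extrusion the only anticipated event, so it does not direct sites towards epiphora.

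No route gives a solicited investigator grade with a *none* level at follow-up.

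**The case against.** **The CRF may already hold an epiphora item.** This is the strongest objection. The CRFs are not in the documents, and the wording of 10.4.3 makes such an item plausible. It stands as a limit: the finding concerns the protocol text. If the item exists, the protocol should still list it and name it as the source.

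**Missing-data rules cover blanks.** Section 7 requires an explanation for all missing data, and section 9 has the monitor check for omissions. Both help if a CRF field exists. Neither creates one.

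**Source documents feed the CRFs.** Section 11.1 says so, and it requires symptom reports at each visit. That narrows the contrast between Visit 1 and follow-up. These remain subject reports, whereas the endpoint is an investigator evaluation.

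**This is an open-label pilot without a sample size calculation.** True, and it limits the consequence. But sections 10.2.2 and 10.4.1 still state a hypothesis and two-sided 5% tests, and an endpoint needs a measurement whatever the power.

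A reader might infer three stronger conclusions that the documents do not support:
- *Epiphora is not considered at any visit.* The Visit 1 eligibility check covers it, without a grade.
- *The secondary ITT set could be empty.* The rule in 10.4.3 lists three kinds of evaluation and can be read so that any one qualifies a subject. The Visit 1 insertion evaluation would then admit every subject with a plug inserted.
- *The number of missed cases, or a maximum number of affected visits, can be stated.* The documents give no epiphora rate or recording rate. Subjects who withdraw or who are discontinued or disqualified are replaced (5.5, 5.5.1.2, 5.5.1.3), so follow-up visits have no fixed ceiling at two per planned subject.

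**Conclusion.** The point holds for the protocol text. An endpoint that carries the only secondary hypothesis has no scheduled evaluation at any of the 3 post-insertion contacts, no graded one at Visit 1, no scale and no named data source.

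Unless the CRFs carry a graded epiphora item, blanks at follow-up cannot be classified and the frequency and severity result is unreliable. It is also likely to miss cases, because detection would rest on a general question and incidental observation. That direction is a judgement; its size cannot be derived from the documents.

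The effect is confined to this secondary endpoint, and the primary tear lake comparison is unaffected. The omission should be fixed, but it does not undermine the study as a whole.

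**What to change.** 1. Add one graded investigator evaluation of epiphora in the study eye, with an explicit *none* level, at Visits 1, 2 and 3 in the synopsis lists, section 7.3 and both Schedules, and at early exit in 7.3.5. Use one scale throughout and define it in 7.2.1.
2. Name that item in 10.4.3 as the data source for the endpoint. If a CRF item already exists, cite it there.
3. State in 10.2.2 and 10.4.3 that, because epiphora in the study eye is excluded at baseline, the comparison amounts to post-insertion incidence and severity.

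The cost is one CRF line per existing visit plus protocol wording, with no new visits or subjects.

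A separate matter should be reconciled on its own: exclusion criteria (a), (c), (d), (e) and (g) refer to the planned study eye in the synopsis and to either eye in section 5.3. Correcting (g) alone would leave the conflict in the other four.

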10.4.4 Safety Analyses

All study subjects who were inserted with a punctal plug will be evaluable for safety analysis. The safety endpoints in this study are clinically significant slit lamp biomicroscopy findings (lid, conjunctiva, and cornea), incident rate of plug extrusions, and the frequency and severity of any reported adverse device events. Safety variables will be summarized using descriptive statistics.

The type, severity, duration and frequency of reported adverse device events will be tabulated by visit. Additionally, any adverse device event experienced by a subject after signing informed consent and before exposure will be presented separately in the safety analysis.

Adverse device events will be coded using the Medical Dictionary for Regulatory Activities (MedDRA). Treatment emergent ADEs (those occurring after insertion of a study punctal plug) will be summarized descriptively: The number and percentage of study subjects who experienced an ADE and the total number of ADEs will be summarized by system organ class and preferred term. Associated ADEs, defined as ADEs suspected to be treatment related by the investigator, SADEs and serious associated ADEs will also be summarized, if necessary. Summaries of each type of event will be prepared by severity and for all severities combined.

Concomitant medication recorded and used during the study will be coded using the World Health Organization Drug Dictionary and listed by subject. Ocular concomitant medications will be identified by each eye in the listing.

10.4.5 Baseline Descriptive Statistics

Demographic and baseline characteristics will be summarized. Counts and percentages will be presented for categorical variables such as sex, age group (by decade), race and ethnicity. Mean, standard deviation, median, minimum and maximum will be presented for continuous variables such as age and non-dilated punctum size.

10.4.6 Planned Interim Analyses

Data will be analyzed on an ongoing basis. The final analyses will be completed after the last study subject has completed his/her final visit and the study database has been closed.

10.5 Sample Size

Since this is a pilot study, no formal sample size estimation was performed.

10.5.1 Enrollment Procedures

Qualified subjects that meet all inclusion and exclusion criteria and complete the screening process will be sequentially assigned a study number.

11 SOURCE DOCUMENTS AND ACCESS

11.1 Source Documentation

The Investigator must maintain adequate and accurate source documents upon which CRFs for each study subject are based. They are to be separate and distinct from the CRFs, except for cases in which the Sponsor has predetermined that direct data entry into specified pages of the subject's CRF is appropriate. Study source documents should include detailed notes on:

- a. Study protocol number
- b. The oral and written communication with the study subject regarding the study treatment (including the risks and benefits of the study).
- c. The date that informed consent and HIPAA forms were signed must be recorded in the source documentation
- d. The study subject's medical history prior to participation in the study
- e. The study subject's basic identifying information, such as demographics, that links the subject's source documents with the CRFs
- f. Date of all study subject visits
- g. Date a punctal plug was first inserted, removed and if applicable, dates of any plug that was extruded/loss
- h. Subject reports of signs and symptoms at each visit

- i. All ADEs and SADE
- j. The subject's exposure to any concomitant therapy (including start and stop dates, route of administration, and dosage)
- k. All relevant observations and data on the condition of the subject throughout the study.

11.2 Access and Retention of Study Records

The study is subject to audits by the Sponsor/designee, third parties, or by regulatory authorities. If such an audit occurs, the Investigator must agree to allow access to all required study subject records. The Investigator will notify Sponsor promptly of any FDA audits that are scheduled, and must forward copies of any resultant Form 483 and/or audit reports to the Sponsor promptly.

All study records will be maintained by the Investigator at the site for a minimum of 2 years following the date a marketing application is approved for the device for which the indication was being investigated. If no application is to be filed or the application is not approved for such indication, study records must be retained for at least 2 years after the investigation is discontinued and the FDA is notified.

